5.3 Post-vaccination Visit(s)

Post-vaccination visits will be performed on:

Follow on subjects: 5 days after the vaccination to collect the blood sample, 30 days after the vaccination to evaluate the subject's safety and to collect the blood sample.

Naive subjects: 30 days after the first vaccination to collect a blood sample and evaluate the subject's safety and 5 days after the second vaccination (Day 66) to collect the blood sample and 30 days (**D**ay 91) after the second vaccination to evaluate the subject's safety and to collect the blood sample.

5.3.1 Follow-up Clinic Visit(s)

Safety follow-up clinic visits will be performed on **D**ay 31 after each vaccination (follow on subjects at Day 31 and the naive subjects at **D**ay 31 and **D**ay 91).

During the follow-up clinic visit, the Subject eDiary will be reviewed. No changes to the information recorded within the Subject eDiary are permissible. For details on the Subject eDiary see sections 3.4.2, Tools Used for Data Collection and 5.2.1 Post-vaccination Procedures. The subject or parent(s)/legal guardian(s) will be interviewed to determine if any unsolicited adverse events occurred and if any concomitant medications or vaccines were taken/received in the time since the last clinic visit. This interview will follow a script which will facilitate the collection of relevant safety information. The healthcare professional reviewing these data will discuss the symptoms (if any) reported by the subject and will determine if any additional diagnoses and/or adverse events are present. Adverse events reported by the subject or parent(s)/legal guardian(s) at this follow-up clinic visit must be recorded in the subject's source document and on an Adverse Events eCRF, as specified in section 7.1, Safety Assessment, and not written on the script used for the interview.

Perform a brief symptom-directed physical examination if necessary according to symptoms the subject has reported. This is a physical examination that will include an

examination of organ systems that are relevant to the investigator based on review of the subject's reported adverse events, concomitant medication use This assessment may include: measurement of vital signs, body temperature (specify route) and a check of general appearance. Measure the subject's height and weight. The physical assessment must be performed by the investigator or designee of the investigator, who is qualified to perform a physical assessment in accordance with their institutional policy.

Corresponding information is documented in the subject's source document and eCRF(s).

The site should schedule the next study activity clinic visit OR safety call] with the subject [and/or parent(s)/legal guardian(s).

The subject and/or parent(s)/legal guardian(s) will receive a written reminder of the next planned study activity. The subject [and/or parent(s)/legal guardian(s)] will be reminded to complete the Subject eDiary and to contact the site if there are any questions and to contact the site immediately (or as soon as the subject is medically stable) if the subject has a medical condition that leads to a hospitalization or an emergency room visit.

(Amended 4 April 2018)

5.3.2 Safety Follow-up Calls

Safety follow-up calls will be performed on Day 16 after each vaccination (all subjects at **D**ay 16 and the naive subjects at **D**ay 76). At least 3 attempts should be made to reach the subject or subjects's parent/legal guardian.

Safety follow-up calls are calls made to the subject or subject's parent/legal guardian by a healthcare professional designated on the site log. These calls will follow a script which will facilitate the collection of relevant safety information. The subject or parent(s)/legal guardian(s) will be interviewed according to the script, and information relating to unsolicited adverse events (AEs), serious adverse events (SAEs), medically attended adverse events, AEs leading to withdrawal, and concomitant medications or vaccinations associated with those events. All safety information described by the subject must be written down in a designated location within the source document and not written on the script used for the telephone call. The site should schedule the next study activity (clinic visit) with the subject or parent(s)/legal guardian(s).

The subject and/or parent(s)/legal guardian(s) will be reminded to contact the site if there are any questions and to contact the site immediately (or as soon as the subject is medically stable) if the subject has a medical condition that leads to a hospitalization or an emergency room visit.

(Amended 4 April 2018)

5.4 Unscheduled Visits

An unscheduled visit describes a non-routine study visit triggered by a specific event. These could include anticipated or unanticipated adverse events or interventions.

5.5 Study Termination Visit

The planned study termination visit will occur on **D**ay 181 for the follow on subjects and at **D**ay 241 for the naive subjects (6 months after the last vaccination), and will be performed by telephone call. However, in case of early terminations, the termination visit may be a clinic visit or a telephone call. The date of termination is the date of the last contact (clinic visit or telephone call) in which the subject's health status was assessed or, in cases where the subject does not agree to any further safety follow-up, it is the date consent is withdrawn. This date should be recorded on the termination eCRF page. For visit procedures to be performed for a subject whose planned study participation ends prematurely, please see section 5.5.1, Early Termination Visit.

During the telephone call (at **D**ay 181 for the follow on subjects and **D**ay 241 for the naive subjects), the following procedures will be performed: Collect medically-attended AEs, SAEs, and concomitant medications for these events.

The site will review with the subject and/or parent(s)/legal guardian(s) the plan of when information relating to the subject's participation in the study may be available (e.g., study results, treatment assignments). It will also be discussed how information relating to the subject's participation in the study will be shared with the subject's healthcare provider, if the subject and/or parent(s)/legal guardian(s) chooses to share this information.

The site will complete the termination eCRF page and this will mark the completion of the subject's participation in the study.

(Amended 4 April 2018)

5.5.1 Early Termination Visit

When a subject is withdrawn from treatment or withdraws from the study, the investigator will notify the Sponsor and, when possible, will perform the procedures listed below. The reason(s) for the early termination will be included in the subject's source documentation. If the Early Termination Visit is a telephone call, collect as much information as possible. Early Termination Visits include subjects who were randomized but not treated.

At the clinic visit or during the telephone call, the following procedures will be performed:

The date of termination from the study is the date of the last contact (clinic visit or telephone call) in which the subject's health status was assessed or, in cases where the subject does not agree to any further safety follow-up, it is the date consent is withdrawn. This date should be recorded on the termination eCRF page.

When a subject is withdrawn from treatment or withdraws from the study, the investigator will notify the Sponsor and, when possible, will perform the procedures listed below. The reason(s) for the early termination will be included in the subject's source documentation. If the Early Termination Visit is a telephone call, collect as much information as possible. Early Termination Visits include subjects who were randomized but not vaccinated.

At the clinic visit or during the telephone call, the following procedures will be performed:

- review solicited AEs collected using eDiary (if applicable) and collect the eDiary device (or schedule a contact to return device to the site, if applicable);
- interview of subject / subject's parent/legal guardian to collect unsolicited adverse events (if applicable for the study period), medically attended adverse events, AEs leading to withdrawal from the study and SAEs;
- interview of subject / subject's parent/legal guardian to collect concomitant medications/ vaccinations;
- perform symptom-directed physical assessment including any organ system warranting further examination based on reporting AEs (if applicable):
- collect blood sampling for immunogenicity assessment (if requested by the protocol at the time of the study termination).

The site will review with the subject and/or parent/legal guardian the plan of when information relating to the subject's participation in the study may be available (e.g., study results, treatment assignments). It will also be discussed how information relating to the subject's participation in the study will be shared with the subject's healthcare provider, if the subject and/or parent/legal guardian chooses to share this information.

The site will complete the termination eCRF page and this will mark the completion of the subject's participation in the study.

The site will review with the subject and/or parent(s)/legal guardian(s) the plan of when information relating to the subject's participation in the study may be available (e.g., study results, treatment assignments). It will also be discussed how information relating to the subject's participation in the study will be shared with the subject's healthcare

Confidential

Protocol V102_15E1 Page 65 of 142

provider, if the subject and/or parent(s)/legal guardian(s) chooses to share this information.

The site will complete the termination eCRF page and this will mark the completion of the subject's participation in the study.

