3.7 Data Monitoring Committee

No Data Monitoring Committee will be convened for this study.

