3.8 Premature Withdrawal from Study

Subjects may withdraw at any time, or be dropped from the study at the discretion of the investigator should any untoward effects occur and/or for safety reasons. In addition, a subject may be withdrawn by the investigator or the Sponsor if he/she violates the study plan or for administrative reasons. The investigator or study coordinator must notify the Sponsor immediately when a subject has been withdrawn due to an adverse event.

The circumstances above are referred to as premature withdrawal from the study, and the reason for premature withdrawal should be clearly documented and detailed in the source documentation. The investigator should make every attempt to evaluate the subject's safety, including resolution of ongoing AEs, at the time of premature withdrawal. If a subject wants to withdraw from the study before all doses are administered or prior to the last planned study visit, the subject will be asked to be followed for safety for the duration of the study. When a subject withdraws, or is withdrawn, from the study, the procedures described in section 5.5.1, Early Termination Visit should be completed if possible.

The reasons for premature withdrawal from the study include: Adverse event, death, withdrawal of consent, lost to follow-up, administrative reason, and protocol deviation. These reasons are described in greater detail below.

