3.8.6 Protocol Deviation

A protocol deviation is any change, divergence, or departure from the study design or procedures of a study protocol. In general, subjects associated with protocol deviations may remain in the study unless continuation in the study jeopardizes the subject's health, safety, or rights.

Investigators will apply due diligence to avoid protocol deviations. Under no circumstances should the investigator contact GSK or its agents, if any, monitoring the study to request approval of a protocol deviation, as no authorized deviations are permitted. If the investigator feels a change to the protocol would improve the conduct of the study this must be considered a protocol amendment, and unless such an amendment is agreed upon by GSK and approved by the IRB/EC and health authorities it cannot be implemented.

Any subject who becomes pregnant during the study, despite the protocol requirement for adequate contraception, will not receive further vaccination (s) but should be encouraged to continue participating in the study for safety follow-up. The site must complete a Pregnancy Report eCRF (initial report) as soon as possible after learning of pregnancy occurrence (see section 7.1.6, Pregnancies for further details). If the subject withdraws from the study for any of the above categories except death, the site will obtain permission from the subject to continue to remain in contact with her until the outcome of the pregnancy is known, even if the outcome is not known until after the subject reaches the end of follow-up period.

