4.3 Criteria for Delay of Vaccination

After enrollment, subjects may encounter clinical circumstances that warrant a delay in subsequent study vaccination. These situations are listed below. In the event that a subject meets a criterion for delay of vaccination, the subject may receive study vaccination once the window for delay has passed as long as the subject is otherwise eligible for study participation.

- Acute moderate or severe infection with or without fever within 3 days of intended study vaccination.
- Fever is defined as body temperature ≥38.0° C within 3 days of intended study vaccination.
- Administration of any vaccine not foreseen by the study protocol within 14 days prior to first vaccination and, if applicable, 7 days prior to the second study vaccination.

Prior to receipt of repeat study vaccination, subjects must be evaluated to confirm that they are eligible for subsequent vaccination. If subjects meet any of the criteria listed below, they should not receive additional vaccinations:

- Subjects who experienced any immediate allergic reaction after the previous study vaccination.
- Subjects who experience any serious adverse event judged to be possibly or probably related to study vaccination, including hypersensitivity reactions.
- Subjects who develop any clinically significant medical condition which, in the opinion of the investigator, may pose additional risk to the subject if he/she continues to participate in the study.
- Subjects who are pregnant.

Subjects who meet any of these criteria must not receive further study vaccinations. However, these subjects should be encouraged to continue study participation, as discussed in section 3.7.

There is clinical circumstance that warrants delay of blood collection for immunogenicity assessments in this study. This situation is listed below. In the event that a subject meets a criterion for delay of blood collection, blood collection may proceed once the window for delay has passed.

• Subject has received a dose of systemic antibiotics less than 3 days before the intended blood collection.

Under such circumstances, a subject may be considered eligible for study enrolment after the appropriate window for delay has passed and inclusion/exclusion criteria have been rechecked, and if the subject is confirmed to be eligible.

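### Protocol 5.5.1 applies the study-termination procedure to a subject who only stops vaccination, which conflicts with 3.8, 3.8.6, 4.3 and 5.5, so safety follow-up can be cut short in naive subjects whose second dose is withheld

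*Protocol*

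**What the plan says.** Protocol 5.5.1 sets out what happens at early termination. Its trigger, stated twice, is: "When a subject is withdrawn from treatment or withdraws from the study, the investigator will notify the Sponsor". It assigns a study termination date ("The date of termination from the study is the date of the last contact") and ends with: "The site will complete the termination eCRF page and this will mark the completion of the subject's participation in the study". It makes no exception for a subject withdrawn from treatment only.

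Four other places bear on the same subjects:

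- **Section 4.3** bars further vaccination after an immediate allergic reaction, after an SAE judged possibly or probably related, for a new significant condition that adds risk, or in pregnancy: "Subjects who meet any of these criteria must not receive further study vaccinations". It continues: "However, these subjects should be encouraged to continue study participation, as discussed in section 3.7".
- **Section 3.8.6** deals with pregnancy only. Such a subject "will not receive further vaccination (s) but should be encouraged to continue participating in the study for safety follow-up".
- **Section 3.8** directs to 5.5.1 only subjects who leave the study, by their own choice or otherwise; it does not mention withdrawal from treatment.
- **Section 5.5** likewise describes 5.5.1 as the procedure for participation that ends early.

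Section 3.7, to which 4.3 points for continued participation, reads in full: "No Data Monitoring Committee will be convened for this study".

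**The concern.** Stopping vaccination and leaving the study are different events, and the analysis depends on keeping them apart. Protocol 8.1.2.3 counts SAEs, medically attended AEs and AEs leading to premature study withdrawal up to Day 241 in naive subjects. A site following 5.5.1 for a subject whose second dose is withheld would complete the termination page and end scheduled contact. A site following 4.3 would try to keep the subject in.

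Under 5.5.1 the subjects who lose follow-up are selected largely by a suspected reaction or a new medical condition, so the shortened observation would be related to safety. The SAP would not bring this to light. Its section 6.1 does not treat premature termination, or the assessments missing after it, as a protocol deviation. Its section 8.2.2 assumes missing immunogenicity values are missing completely at random.

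**Working it through.** The plan states no figure on this point. The check is a comparison of passages and a subtraction of visit days.

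**Which rule applies to a subject barred from dose 2 who has not withdrawn?**

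| Section | Applies to | Consequence |
|---|---|---|
| 5.5.1 | withdrawn from treatment, or leaving the study | termination page; participation ends |
| 4.3 | barred from further vaccination (four criteria) | encouraged to continue |
| 3.8.6 | pregnant | no further vaccination; encouraged to stay for safety follow-up |
| 3.8 | leaving the study | go to 5.5.1 |
| 5.5 | participation ending early | go to 5.5.1 |

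Taken literally, this subject meets the first trigger of 5.5.1 and also falls under 4.3. The consequences are opposite. The text that should settle it is the target of the 4.3 cross-reference, and that target is unrelated.

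**Who is exposed?** Follow-on subjects receive one dose, so nothing remains to be withheld after it. Naive subjects receive doses at Day 1 and Day 61: 200 planned, randomized 1:1, so 100 per arm. One subject is 1/100 = 1% of an arm. The documents give no expected number barred from dose 2.

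**What would be lost if the subject were closed at Day 61?** From Protocol Table 6:

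- Clinic visits at Days 66 and 91, both with serum draws.
- Safety calls at Days 76, 151 and 241.
- Follow-up obtained after dose 1: 61 − 1 = 60 days.
- Follow-up lost against the planned last contact: 241 − 61 = 180 days, which is 180/240 = 75% of the planned period.

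The stated aim is safety follow-up for six months after the last vaccination, which the plan realizes as 241 − 61 = 180 days. For a subject with dose 1 only, six months ends at about Day 1 + 180 = Day 181. The loss on that basis is 181 − 61 = 120 days. The naive schedule has no contact at Day 181; the calls on either side are at Days 151 and 241.

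**What would still be captured?**

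- Ongoing AEs are followed to resolution or stabilization (3.8.1, 7.1.3).
- Pregnancies are followed to outcome if the subject agrees, even after follow-up ends (3.8.6, 7.1.6).
- SAEs considered caused by the vaccine remain reportable outside the follow-up period (7.1.5.1).

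What remains uncollected is new medically attended AEs, SAEs not considered vaccine-caused, and the Day 66 and 91 serum. The early termination visit would not replace the serum, because 5.5.1 takes blood only if a draw is due at that time and none is scheduled for naive subjects at Day 61. The serum has some value: the Full Analysis Set definition for Days 66 and 91 (SAP 7.3) requires at least one vaccination, not two, so a retained subject who gave the required samples could contribute.

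**The case against.** The best defence is that the protocol should be read as a whole. Section 4.3 is the specific provision for these subjects and it favours keeping them. Sections 3.8 and 5.5 both tie 5.5.1 to leaving the study. Section 3.8 asks a subject who wants to leave before all doses to be followed for safety, and 3.8.3 has the investigator establish whether a withdrawal of consent is complete or partial. The mention of treatment in 5.5.1 may be aimed at subjects randomized but never vaccinated, whom 5.1.4 also calls early terminations. Safety is descriptive, with no hypothesis or success criterion.

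Much of this stands. It makes the harmful reading less likely, but no sentence excludes it. The request in 3.8 concerns a subject who wishes to leave, not one whose dose is withheld. The layout also invites confusion: the bars on vaccination for a related SAE (3.8.1) and for pregnancy (3.8.6) both sit under the heading of premature withdrawal from the study.

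A reader might infer three stronger things that the documents do not support:

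- **That all later safety information on these subjects disappears.** The provisions in 3.8.1, 7.1.3, 7.1.5.1 and 7.1.6 rule that out.
- **That the count of AEs leading to withdrawal turns wholly on which section a site follows.** Section 7.1.3 defines these as leading to study or vaccine withdrawal, so an AE that stops dose 2 qualifies either way. The endpoint in 8.1.2.3 is worded for study withdrawal only, so some ambiguity stays, but it does not come from 5.5.1 alone.
- **That the protocol requires these subjects to continue, or that sites will in fact differ.** The text says encouraged, and site practice is unknown.

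**Conclusion.** The inconsistency is real and in the current text. Followed as written, 5.5.1 ends scheduled data collection for a subject whom 4.3 would encourage to stay.

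The size is bounded. It concerns only naive subjects barred from dose 2, in unknown number. Per subject closed at Day 61 it costs two visits, three calls and between about 120 and 180 days of follow-up, depending on whether the yardstick is six months after dose 1 or the Day 241 contact. The 75% figure is the upper of these two. Closure before Day 61 would lose more.

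The primary endpoint is not affected, because it uses the Day 1 sample taken before vaccination. The effect is on secondary safety summaries to end of study, on Day 66 and 91 serology, and on disposition. It rests on the assumption that a site applies 5.5.1 literally; the documents make that possible, not certain. The correction is worth making because the loss would fall selectively on subjects stopped for safety and costs very little to prevent.

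**What to change.** Reconcile 5.5.1 with 3.8, 3.8.6, 4.3 and 5.5:

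1. Give stopping vaccination and leaving the study distinct data-collection procedures and distinct eCRF consequences, so that disposition can be tabulated without interpretation.
2. State which of the scheduled safety contacts, and up to which day, apply to a subject who stops vaccination but stays in the study. The sponsor has to settle this, because the planned Day 241 contact and six months after the last dose received do not coincide for a single-dose subject.
3. Correct the cross-reference in 4.3, which now leads to section 3.7, so that it points to text on continued participation.

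Eligibility for vaccination and clinical management are left as they are. The cost is protocol wording and a clarification to sites. The contacts are already on the naive schedule, so no visit need be added.
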